4.1.2 Exclusion Criteria

Patients will be excluded from enrollment in specific arms if they meet any of the applicable criteria outlined in subsequent sections, as summarized by treatment arm in [Table 5](#).

Table 5 Arm-Specific Exclusion Criteria

Cohort	Treatment Arm	Applicable Exclusion Criteria
1	Nivo + Ipi (control)	Sections 4.1.2.1 and 4.1.2.2
	RO7247669 2100 mg	Sections 4.1.2.1 , 4.1.2.2 , and 4.1.2.4
	Atezo + Tira	Sections 4.1.2.1 , 4.1.2.2 , and 4.1.2.5
	RO7247669 2100 mg + Tira	Sections 4.1.2.1 , 4.1.2.2 , 4.1.2.4 , and 4.1.2.5
	RO7247669 600 mg	Sections 4.1.2.1 , 4.1.2.2 , and 4.1.2.4
	RO7247669 600 mg + Tira	Sections 4.1.2.1 , 4.1.2.2 , 4.1.2.4 , and 4.1.2.5
2	RO7247669 2100 mg + Tira	Sections 4.1.2.1 , 4.1.2.3 , 4.1.2.4 , and 4.1.2.5

Atezo = atezolizumab; Ipi = ipilimumab; Nivo = nivolumab; Tira = tiragolumab.

4.1.2.1 Exclusion Criteria for Cohort 1 and Cohort 2

Patients who meet any of the following criteria will be excluded from study entry:

- Mucosal and uveal melanoma

Acral lentiginous melanoma is excluded for Cohort 1.

For Cohort 2, acral lentiginous melanoma is permitted; however, the proportion of patients should not exceed 20% of response-evaluable patients.

- Treatment with investigational therapy within 28 days prior to initiation of study treatment
- Treatment with systemic immunostimulatory agents (including, but not limited to, IFN and IL-2) within 4 weeks or 5 drug-elimination half-lives (whichever is longer) prior to initiation of study treatment
- Prior allogeneic stem cell or solid organ transplantation
- Known immunodeficiency or conditions requiring treatment with systemic immunosuppressive medication (including, but not limited to, cyclophosphamide, azathioprine, methotrexate, thalidomide, and anti-tumor necrosis factor- α agents), or anticipation of need for systemic immunosuppressant medication during study treatment, with the following exceptions:

Patients on replacement doses of corticosteroids to manage hypopituitary or adrenal insufficiency are eligible for the study.

Patients who received acute, low-dose, systemic immunosuppressant medications, or a one-time pulse dose of systemic immunosuppressant medication (e.g., 48 hours of corticosteroids for a contrast allergy) are eligible for the study. Patients requiring chronic low-dose systemic corticosteroid treatment (i.e., a maximal dose of corticosteroids \leq 10mg/day equivalent prednisone) are eligible.

Patients who received mineralocorticoids (e.g., fludrocortisone), corticosteroids for chronic obstructive pulmonary disease or asthma, or low-dose corticosteroids for orthostatic hypotension or adrenal insufficiency are eligible for the study.

- Treatment with a live, attenuated vaccine within 4 weeks prior to initiation of study treatment, or anticipation of need for such a vaccine during study treatment or within 5 months after the final dose of study treatment
- Active or history of autoimmune disease or immune deficiency, including, but not limited to, myasthenia gravis, myositis, autoimmune hepatitis, systemic lupus erythematosus, rheumatoid arthritis, inflammatory bowel disease, antiphospholipid antibody syndrome, Wegener granulomatosis, Sjögren syndrome, Guillain-Barré syndrome, or multiple sclerosis (see [Appendix 7](#)) for a more comprehensive list of autoimmune diseases and immune deficiencies), with the following exceptions:

Patients with a history of autoimmune-related hypothyroidism who are on thyroid-replacement hormone are eligible for the study.

Patients with controlled Type 1 diabetes mellitus who are on a stable insulin regimen are eligible for the study.

Patients with eczema, psoriasis, lichen simplex chronicus, or vitiligo with dermatologic manifestations only (e.g., patients with psoriatic arthritis are excluded) are eligible for the study provided all of following conditions are met:

- Rash must cover $<10\%$ of body surface area.
- Disease is well controlled at baseline and requires only low-potency topical corticosteroids.
- There is no occurrence of acute exacerbations of the underlying condition requiring psoralen plus ultraviolet A radiation, methotrexate, retinoids, biologic agents, oral calcineurin inhibitors, or high-potency or oral corticosteroids within the previous 12 months.
- History of idiopathic pulmonary fibrosis, organizing pneumonia (e.g., bronchiolitis obliterans), drug-induced pneumonitis, or idiopathic pneumonitis, or evidence of active pneumonitis on screening chest computed tomography (CT) scan. Patients with a history of CIT-related pneumonitis Grade <2 are eligible.
- History of malignancy other than malignant melanoma within 2 years prior to screening, with the exception of malignancies with a negligible risk of metastasis or death (e.g., 5-year OS rate $>90\%$), such as adequately treated carcinoma in situ of the cervix, non-melanoma skin carcinoma, localized prostate cancer, ductal carcinoma in situ, or Stage I uterine cancer

- Active tuberculosis (TB)
- Severe infection within 4 weeks prior to initiation of study treatment, including, but not limited to, hospitalization for complications of infection, bacteremia, or severe pneumonia, or any active infection that, in the opinion of the investigator, could impact patient safety
- Treatment with therapeutic or prophylactic oral or IV antibiotics within 2 weeks prior to initiation of study treatment
- Significant cardiovascular disease such as New York Heart Association cardiac disease (Class II or greater), myocardial infarction or cerebrovascular accident within 3 months prior to initiation of study treatment, unstable arrhythmia, or unstable angina
- Uncontrolled hypertension (defined as resting systolic blood pressure > 150 mmHg and/or diastolic blood pressure > 100 mmHg in two or more serial measurements)
- Major surgical procedure, other than for diagnosis, within 4 weeks prior to initiation of study treatment, or anticipation of need for a major surgical procedure other than CLND, during the study

Placement of central venous access catheter (e.g., port or similar) is not considered a major surgical procedure and is therefore permitted.

- Any other disease, metabolic dysfunction, physical examination finding, or clinical laboratory finding that contraindicates the use of an investigational drug, may affect the interpretation of the results, impair the ability of the patient to participate in the study, or may render the patient at high risk from treatment complications
- History of severe allergic reactions to chimeric or humanized antibodies or fusion proteins
- Known hypersensitivity to Chinese hamster ovary cell products or recombinant human antibodies
- Known allergy or hypersensitivity to any of the study drugs or their excipients
- Known intolerance to any of the drugs required for premedication (acetaminophen, ranitidine, diphenhydramine, and methylprednisolone)
- Pregnancy or breastfeeding, or intention of becoming pregnant during the study

Women of childbearing potential must have a negative serum pregnancy test result within 14 days prior to initiation of study treatment.

- Eligible only for the control arm

4.1.2.2 Exclusion Criteria for Cohort 1

Patients who meet any of the following criteria will be excluded from Cohort 1:

- Distantly metastasized melanoma
- History of in-transit metastases within the last 6 months
- Prior radiotherapy

- Prior immunotherapy, including anti-CTLA-4, anti-PD-1, and anti-PD-L1 therapeutic antibodies, and other systemic therapy for melanoma

4.1.2.3 Exclusion Criteria for Cohort 2

Patients who meet any of the following criteria will be excluded from Cohort 2:

- Symptomatic, untreated, or progressing CNS metastases

Asymptomatic patients with treated CNS lesions are eligible, provided that all of the following criteria are met:

- Measurable disease, per RECIST v1.1, must be present outside the CNS.
- The patient has no history of intracranial hemorrhage or spinal cord hemorrhage.
- CNS metastases are stable for ≥ 4 weeks prior to initiation of study, or neurosurgical resection occurred ≥ 28 days prior to initiation of study treatment.
- The patient has no requirement for corticosteroids as therapy for CNS disease for at least 14 days prior to initiation of study treatment.
- Anti-convulsant therapy at a stable dose is permitted.
- Active or history of carcinomatous meningitis/leptomeningeal disease
- Uncontrolled tumor-related pain

Patients requiring pain medication must be on a stable regimen at screening.

Symptomatic lesions (e.g., bone metastases or metastases causing nerve impingement) amenable to palliative radiotherapy should be treated prior to enrollment. Patients should be recovered from the effects of radiation. There is no required minimum recovery period.

Asymptomatic metastatic lesions that would likely cause functional deficits or intractable pain with further growth (e.g., epidural metastasis that is not currently associated with spinal cord compression) should be considered for loco-regional therapy, if appropriate, prior to enrollment.

- Uncontrolled pleural effusion, pericardial effusion, or ascites requiring recurrent drainage procedures (once monthly or more frequently)
 - Patients with indwelling catheters (e.g., PleurX[®]) are allowed.
- Uncontrolled or symptomatic hypercalcemia (ionized calcium > 1.5 mmol/L, calcium > 12 mg/dL, or corrected calcium $>$ ULN)
- Any history of an immune-mediated Grade 4 adverse event attributed to prior CIT (other than endocrinopathy managed with replacement therapy or asymptomatic elevation of serum amylase or lipase) that resulted in permanent discontinuation of the prior immunotherapeutic agent

- All immune-mediated adverse events related to prior immunomodulatory therapy (other than endocrinopathy managed with replacement therapy or stable vitiligo) that have not resolved completely to baseline. Patients treated with corticosteroids for immune-mediated adverse events, except for corticosteroids replacement therapy for adrenal insufficiency (provided that the patient receives ≤ 10 mg prednisone/day or equivalent), must not have related symptoms or signs for ≥ 4 weeks following discontinuation of corticosteroids
- Adverse events related to any prior radiotherapy, chemotherapy, targeted therapy, CPI therapy or surgical procedure must have resolved to Grade 1 or better, except alopecia (any grade), Grade 2 peripheral neuropathy, and hypothyroidism and/or hypopituitarism on a stable dosage of hormone replacement therapy (e.g., thyroxine, hydrocortisone, prednisolone, others)

4.1.2.4 Exclusion Criteria for RO7247669-Containing Arms (Cohort 1 and Cohort 2)

Patients who meet any of the following criteria will be excluded from the RO7247669-containing arms:

- Prior treatment with an anti-LAG-3 agent
- History of myocarditis (regardless of etiology)
- Left ventricular ejection fraction (LVEF) $< 50\%$ assessed by either transthoracic echocardiogram (TTE) or multiple-gated acquisition (MUGA) scan (TTE preferred test) within 6 months prior to initiation of study treatment
- Troponin T (TnT) or troponin I (TnI) $>$ institutional ULN

Patients with TnT or TnI levels between > 1 and $< 2 \times$ ULN are eligible if repeat levels within 24 hours are $\leq 1 \times$ ULN. If repeat levels within 24 hours are between > 1 and $< 2 \times$ ULN, patients need to undergo a cardiac evaluation and may be considered for treatment if there are no clinically significant findings.

4.1.2.5 Exclusion Criteria for Tiragolumab-Containing Arms (Cohort 1 and Cohort 2)

Patients who meet any of the following criteria will be excluded from the tiragolumab-containing arms:

- Prior treatment with an anti-TIGIT agent
- Acute Epstein-Barr virus (EBV) infection or known or suspected chronic active EBV infection at screening

Patients with a positive EBV viral capsid antigen (VCA) IgM test at screening are excluded from this arm. An EBV PCR test should be performed as clinically indicated to screen for active infection or suspected chronic active infection. Patients with a positive EBV PCR test are excluded from this arm.

4.2 METHOD OF TREATMENT ASSIGNMENT

This is a randomized, open-label study. After initial written informed consent has been obtained, all screening procedures and assessments have been completed, and eligibility has been established for a patient, the study site will obtain the patient's identification number and treatment assignment from the interactive web-based response system (IxRS).

For Cohort 1, this study will employ a permuted-block randomization method with dynamically changing randomization ratios to account for fluctuation in the number of treatment arms that are open for enrollment over the course of the study.

The randomization ratio will depend on the number of experimental arms that are open for enrollment (e.g., if an arm is added or enrollment in an arm is suspended pending analysis of results from the preliminary phase), with the stipulation that the likelihood of being allocated to the control arm will be no more than 35%. The randomization ratios may be altered to increase enrollment in a particular arm.

Randomization will be stratified according to the following criteria:

- Geographic region: Australia vs. Rest of the World
- Baseline LDH: \leq ULN vs. $>$ ULN

Randomization will take into account general exclusion criteria and arm-specific exclusion criteria as outlined in Section 4.1.2. For example, the Atezo + Tira arm will be removed as an option for patients who are ineligible for that arm. If a patient is only eligible for the control arm, that patient will not be enrolled in the study.

For Cohort 2, patients will be assigned to receive treatment with RO7247669 2100 mg + Tira. If additional treatment arms are opened at a later time, a permuted-block randomization method will be employed from this point forward.

Patients who do not receive at least one dose of each drug for their assigned treatment regimen will not be included in the efficacy analyses. Additional patients may be enrolled to reach the target number of treated patients planned for analysis.

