4.6.2 Patient Discontinuation from Study

Patients have the right to voluntarily withdraw from the study at any time for any reason. In addition, the investigator has the right to withdraw a patient from the study at any time. Reasons for withdrawal from the study may include, but are not limited to, the following:

- Patient withdrawal of consent
- Study termination or site closure
- Patient non-compliance, defined as failure to comply with protocol requirements as determined by the investigator or Sponsor

Every effort should be made to obtain information on patients who withdraw from the study but have not withdrawn consent. The primary reason for withdrawal from the study should be documented on the appropriate eCRF. Patients who withdraw from the study will not be replaced.

If a patient withdraws from the study, the study staff may use a public information source (e.g., country records) to obtain information about survival status.

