6. STATISTICAL CONSIDERATIONS AND ANALYSIS PLAN

The final study analysis will be based on patient data collected through study discontinuation. If not otherwise specified, efficacy analyses will be based on the efficacy-evaluable population, defined as all patients who receive at least one dose of each drug for their assigned treatment regimen, and safety analyses will be based on the safety-evaluable population, defined as all patients who receive any amount of study treatment.

The analysis results will be summarized by the treatment that patients actually receive. Data will be described and summarized as warranted by sample size. Continuous variables will be summarized through use of means, standard deviations, medians, and ranges. Categorical variables will be summarized through use of counts and percentages. Listings will be used in place of tables in the event of small sample sizes.

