6.4 EFFICACY ANALYSES

6.4.1 Primary Efficacy Endpoint in Cohort 1

The primary efficacy endpoint in Cohort 1 is pRR at time of surgery. pRR will be assessed after completion of neoadjuvant treatment (Week 7) at time of CLND.

The pRR is defined as the proportion of patients who achieve pCR (a complete absence of viable tumor in the treated tumor bed), pathologic near complete response (pnCR; <10% of viable tumor in the treated tumor bed); and pathologic partial response (pPR; <50% of the treated tumor bed is occupied by viable tumor cells) as determined by independent pathologic review. Patients with missing or no pathologic response assessment, *including patients who do not proceed to CLND*, will be classified as non-responders.

pRR will be calculated for each arm along with 95% CIs (Clopper-Pearson method). The difference in pRR between the experimental arms and the control arm will also be calculated, along with 95% CIs using the Wald method with continuity correction.

6.4.2 Secondary Efficacy Endpoints in Cohort 1

The secondary efficacy endpoints in Cohort 1 are pRR at time of surgery as determined by local pathologic assessment, event-free survival (EFS), RFS, OS, and ORR prior to surgery. pRR is defined in Section [6.4.1](#).

EFS is defined as the time from randomization to any of the following events (whichever occurs first): disease progression that precludes surgery, as assessed by the investigator according to RECIST v1.1 (see Section [4.5.7](#)); local, regional, or distant disease recurrence; or death from any cause. Patients who have not experienced such events will be censored at the time of their last post-tumor tumor assessment.

RFS is defined as the time from surgery to the first documented recurrence of disease or death from any cause. For patients who do not have documented recurrence of disease or death, RFS will be censored at the day of the last tumor assessment.

OS is defined as the time from randomization to death from any cause. Patients who are still alive at the time of OS analysis will be censored at the last date they were known to be alive.

The Kaplan-Meier method will be used to estimate the median for RFS, EFS, and OS, 95% CIs will be constructed using the Brookmeyer and Crowley method. The RFS, EFS, and OS rate at specific timepoints will also be estimated using the Kaplan-Meier method, with 95% CIs calculated on the basis of Greenwood's estimate for the variance.

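### The Cohort 1 pRR comparison with control omits randomized patients who never start every assigned drug, a condition harder to meet in two-drug arms than in monotherapy arms

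*Combined protocol and SAP*

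**What the plan says.** Section 4.2 (Method of Treatment Assignment) says that patients who "do not receive at least one dose of each drug for their assigned treatment regimen will not be included in the efficacy analyses". The next sentence allows top-up: "Additional patients may be enrolled to reach the target number of treated patients planned for analysis".

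The opening of Section 6 defines the efficacy-evaluable population in the same terms, "defined as all patients who receive at least one dose of each drug for their assigned treatment regimen", and applies it wherever nothing else is specified. It adds: "The analysis results will be summarized by the treatment that patients actually receive".

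Section 6.4.1 defines the primary pRR analysis in Cohort 1 and says: "The difference in pRR between the experimental arms and the control arm will also be calculated". It names no other population. It does have a rule for missing outcomes: patients with no pathologic assessment, "including patients who do not proceed to CLND*, will be classified as non-responders". Section 6.4.2 has a similar rule for ORR. It times EFS and OS from randomization, again with no other population named.

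Section 4.6.2 says: "Patients who withdraw from the study will not be replaced". The text does not say whether this or the top-up sentence governs a patient who withdraws before dosing.

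**The concern.** Membership of the efficacy set is decided after an open-label assignment. Two kinds of randomized patient drop out of it: those who never start treatment, for instance because they decline the arm they were given, and those who receive one drug of a pair but never the other.

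The second route exists only in two-drug arms. A patient who stops for good after the first infusion in an RO7247669 monotherapy arm is evaluable and counts in the denominator. A patient who stops between the two drugs in Nivo + Ipi, Atezo + Tira or RO7247669 + Tira is not evaluable.

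At stake is whether the difference from control compares the groups that were randomized. Section 1.2 gives the control arm the job of strengthening confidence in signals from the experimental arms. With 20 to 60 patients per experimental arm and 35 to 50 on control (Section 6.1), one or two exclusions are visible in the estimate.

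**Working it through.** **Inputs from the documents.** Arm sizes are in Section 6.1 and Table 4. Background pRR for nivolumab plus ipilimumab is 70%–80% (Section 1.1.2.1). The expansion example in Section 6.9 uses a 10-point pRR improvement and a 70% posterior probability. The confidence interval is Wald with continuity correction (Section 6.4.1).

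**Assumptions.** The documents give no number of patients expected to miss a drug, so 1 or 2 per arm is an illustration only. Section 6.9 names no prior, so Beta(1,1) is assumed.

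**The plan's own figure.** There is no power or exclusion figure to reproduce. The upper Cohort 1 total does reproduce from Table 4: 50 + (20 + 20 + 20 + 40 + 40) + 5 × 20 = 290. Nothing below depends on it.

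**Step 1: who leaves the denominator.**

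| Randomized patient | RO7247669 monotherapy arm | Two-drug arm |
|---|---|---|
| Never dosed | Out | Out |
| First drug only, then stops | In | Out |
| Every drug started, no CLND or pathology | In, non-responder | In, non-responder |

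**Step 2: effect on one arm.** Let n be randomized, x responders, d excluded, and r the responders among the excluded. Reported pRR = (x − r)/(n − d).

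- n = 20, x = 15: 15/20 = 75.0%
- d = 1, r = 0: 15/19 = 78.9%
- d = 2, r = 0: 15/18 = 83.3%
- d = 1, r = 1: 14/19 = 73.7%
- n = 40, x = 30: 30/40 = 75.0%; with d = 2, r = 0: 30/38 = 78.9%

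**Step 3: effect on the difference from control.** The interval is difference ± [1.96 × √(p₁(1−p₁)/n₁ + p₂(1−p₂)/n₂) + ½(1/n₁ + 1/n₂)].

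- Monotherapy 30/40 against control 30/40: 0.0 points (−21.5 to 21.5).
- The same with two control non-responders excluded, 30/40 against 30/38: −3.9 points (−25.2 to 17.3).
- Monotherapy 34/40 against control 28/40: 85.0 − 70.0 = 15.0 points. With two control non-responders excluded: 85.0 − 73.7 = 11.3 points.

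**Step 4: effect on the expansion example.** The quantity is the posterior probability that the difference exceeds 10 points, by simulation under the assumed priors, with control 30/40 and d non-responders excluded from a 20-patient combination arm.

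| Responders | d = 0 | d = 1 | d = 2 |
|---|---|---|---|
| 15 | 0.17 | 0.25 | 0.38 |
| 16 | 0.28 | 0.41 | 0.57 |
| 17 | 0.44 | 0.59 | 0.76 |

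Two exclusions cross 0.70 with 17 responders but not with 15 or 16. In the opposite direction, monotherapy 34/40 against control 28/40 gives 0.68, and two control exclusions lower it to 0.54.

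**The case against.** The strongest reply is that the affected group is small and the bias has no fixed sign. Much of this stands.

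- **Scope.** A reader might infer that treatment failures in general drop out of pRR. They do not: the non-responder rule in Section 6.4.1 still catches everyone who started each drug.
- **Frequency.** Both drugs of a pair are given on Day 1 of each cycle, and one dose in either cycle qualifies. Appendix 9 describes infusion reactions as generally mild to moderate and allows infusions to restart after Grade 1 or 2 cytokine-release syndrome. It does require both drugs to stop permanently at Grade 3 or 4. The number blocked from the second drug cannot be judged from the text.
- **Direction.** A reader might infer that early intolerance always raises the pRR of a poorly tolerated combination. That holds only if the excluded patients would not have responded. Patients who stop for toxicity can still go to CLND (Section 3.1.5), and losing a responder lowers the rate (14/19 = 73.7%). Control is itself a two-drug arm, so against control the unequal gate concerns only the monotherapy arms.
- **Grouping by treatment received.** This adds little, because entry already requires every drug of the assigned regimen.
- **Other safeguards.** Early intolerance appears in the safety set, and disposition is reported by arm (Section 6.2). Expansion under Section 6.9 rests on the totality of data, and Section 6.1 disclaims formal testing.

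None of this supplies an all-randomized efficacy estimate, and the text defines none. Signal-finding aims explain a supportive evaluable set; they do not explain making it the only basis for a randomized difference. Equal gates for control and the experimental combinations also do not ensure equal losses.

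**Conclusion.** The point holds in a limited form. As written, the primary pRR difference in Cohort 1, and EFS and OS timed from randomization, are estimated in a subset formed after open-label assignment, with an entry condition that is harder to meet in two-drug arms. Only undosed and partly dosed patients are affected.

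The size is unknown. Under the illustrative assumption of one or two excluded non-responders, pRR in a 20-patient arm with 15 responders rises by 3.9 or 8.3 points; two exclusions in a 40-patient arm with 30 responders raise it by 3.9. Excluding control non-responders would flatter control against monotherapy. Excluding non-responders from an experimental combination would flatter that combination.

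The documents do not support saying that a stated power or error rate is invalidated, since none is stated, or that an expansion decision would be reversed. The crossing from 0.44 to 0.76 rests on assumed priors and counts, and the rule itself is only an example. This is a worthwhile, inexpensive improvement rather than a defect that invalidates the trial.

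**What to change.** In Sections 4.2, 6 and 6.4, for Cohort 1:

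1. Analyse pRR, ORR and their differences from control in all randomized patients by assigned arm. Apply the existing rule: no pathology or CLND (for pRR), or no response assessment (for ORR), means non-responder. A partly dosed patient who has a result keeps it.
2. Analyse EFS and OS in the same set, using the follow-up available.
3. Keep the set requiring a dose of each drug, as treated, as a supportive analysis.
4. Report the number excluded from that set and the reasons, by arm.
5. Keep the top-up sentence in Section 4.2 for enrolment, but state that a topped-up patient does not remove the original patient from the all-randomized analysis. Cross-refer to Section 4.6.2 so that it is clear which sentence governs withdrawal before dosing.

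The cost is wording and one further set of outputs; enrolment is unchanged. Reported pRR may be slightly lower. EFS and OS may be thin in never-dosed patients, because Section 4.6.1 times the visit for patients without surgery from the final dose.
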